On the morning of Day 1, following an overnight fast of at least 14 hours, subjects will have a final MRS scan performed (T = 24 hours) and blood sampling. On Day -1 or Day 1, eligibility criteria will be verified (the final eligibility check may occur at any time from Day -3 to Day 1) and subjects will be randomised to receive investigational product (MEDI0382 or placebo in Part A or MEDI0382, placebo, or liraglutide in Part B). Following predose safety measures, the subjects will receive their first dose of investigational product via SC injection and will be discharged from the clinical unit with a sufficient supply of investigational product to self-administer once daily by SC injection at home in the morning.

In Part A subjects will return for an outpatient visit at weekly intervals (Day 8 and Day 15) for safety assessments, dose up-titration until a dose of 300 μg MEDI0382 is reached in Part A. Subjects will receive sufficient supply of investigational product at each outpatient visit.

On Day 26 subjects will be re-admitted to the clinical unit for a further 3 nights inpatient stay and as before will receive standardised solid meals during this period. On the evening of Day 27, subjects will fast and be given $^2\text{H}_2\text{O}$ water to drink at 2 times during the overnight period. On Day 28, following an MRS scan and blood sampling, subjects will receive an SC dose of investigational product and then undergo a MMTT as before at T = 0 and serial MRS scans and blood samples will be collected at T = 4, 9, and 14 hours. On Day 29, following an overnight fast, a final MRS scan will be performed alongside a blood test at T = 24 hours.

In Part B subjects will return for an outpatient visit on Day 8 for safety assessments, dose up-titration, and will receive an adequate supply of investigational product. On Days 14/15 and 21/22 remote contacts will be performed to advise on further dose uptitration as required and to collect AE/serious adverse events (SAEs) and concomitant medication information.

On Day 33 subjects will be re-admitted to the clinical unit for a further 3 nights inpatient stay and as before will receive standardised solid meals during this period. On the evening of Day 34, subjects will fast and be given $^2\text{H}_2\text{O}$ water to drink at 2 times during the overnight period. On Day 35, following an MRS scan and blood sampling, subjects will receive an SC dose of investigational product and then undergo a MMTT as

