4.1.6 Discontinuation of Investigational Product

An individual subject will not receive any further investigational product if any of the following occur in the subject in question (applies for both Part A and Part B of the study):

- Withdrawal of consent from further treatment with investigational product or lost to follow-up
- An AE that, in the opinion of the investigator or the sponsor, contraindicates further dosing
- Subject is determined to have met one or more of the exclusion criteria or failed to meet all of the inclusion criteria for study participation at study entry and continuing investigational product, in the decision of the investigator, might constitute a safety risk
- Subject noncompliance that, in the opinion of the investigator or sponsor, warrants withdrawal (eg, refusal to adhere to scheduled visits).
- Pregnancy in a female subject

Subjects who are permanently discontinued from receiving investigational product will be followed for protocol-specified assessments including follow-up of any AEs unless consent is withdrawn from further study participation (Section 4.1.5), the subject is lost to follow-up, the subject starts alternative treatment, or the subject is enrolled in another clinical study.

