^q Investigational product administration should occur in the clinic on Day 1 (Visit 2) after the final MRS scan and blood sample collection (Day 1 first dose of MEDI0382 50 µg or 0.6 mg liraglutide). Daily investigational product administration should then be performed by the subject at home on Day 2 through Day 7 (Day 7 is the last dose of MEDI0382 at a dosage level of 50 µg or liraglutide 0.6 mg). The subject will receive the first dose of MEDI0382 100 µg or liraglutide 1.2 mg in clinic on Day 8 (Visit 3) at any time in the morning. The subject will then self-administer investigational product at home daily on Day 9 through to Day 14 (Day 14 is the last dose of MEDI0382 at a dose level of 100 µg or liraglutide 1.2 mg). On Day 14 or the morning of Day 15 prior to dosing, the site will make remote contact with the subject and remind them to make the up-titration in the MEDI0382 or placebo arms to 200 µg or liraglutide to 1.8 mg and to continue daily dosing at home. On Day 22 subjects in the MEDI0382 or placebo arms will be asked to uptitrate to 300 µg and to continue this dose until their next visit. Subjects in the liraglutide arm will be advised to continue at a dose at 1.8 mg and to continue this dose until their next visit.

^r MEDI0382 or placebo and liraglutide will be dispensed on Days 1 and 8.

^s #Up-titration in blinded arms only

Table 10 Schedule of Treatment Period Study Procedures (Day 32 through Day 36) (Part B)

Visit Number	Outpatient	Treatment Phase				
		V6				
		Inpatient				
Procedure / Study Day	Day 32	Day 33	Day 34	Day 35 ^a	Day 36	
Metformin washout for 5 days ^b	X	X	X	X	X	
Admission to the clinical unit		X				
Assessment of AE/SAEs ^c and review of concomitant medications		X	X	X	X	
Discharge from the clinical unit						X
Fasting overnight for a minimum of 14 hours required			X	X		
Physical examination (abbreviated), ECG, and urine (or serum) pregnancy test		X				
Weight and urinalysis						X
Vital signs (BP, pulse, body temperature, respiratory rate)		X				X
Collection of blood samples for: ^a						
Serum chemistry, haematology, HbA1c, serum calcitonin, amylase, and lipase						X
Fasting amino acids, FFAs, lipids, BHB, acetoacetate and lactate				X		
MEDI0382 Pharmacokinetics ^d				X		
Immunogenicity (ADA) ^e				X		
Blood samples for non-genetic future research ^f				X	X	
Blood samples for ² H labelled glucose ^g			X	X	X	
████████████████ ^h					X	

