^g Blood samples for measurement of 2H labelled glucose should be collected just prior to deuterated water administration on Day 34 at 1800 (± 10 min). Further blood samples for measurement of 2H labelled glucose (along with blood samples for non-genetic testing, see footnote e) should be collected on Day 35 and Day 36 following the 0800 morning standardised liquid meal administered on Day 35 at T = 0, 220 min (± 5 min), 9 hr (± 30 min), 14 hr (± 30 min) and 24 hr. Note that the time of sampling may be adjusted to ± 1 hr provided all other related procedures are performed at the same time intervals.

^h [REDACTED]

Table 10 Schedule of Treatment Period Study Procedures (Day 32 through Day 36) (Part B)

Study Period	Visit Number	Treatment Phase				
		Outpatient	V6			
			Inpatient			
Procedure / Study Day		Day 32	Day 33	Day 34	Day 35 ^a	Day 36

ⁱ Standardised solid meals are to be given to subjects 3 times daily on Day 33 and Day 34 at 0900 (\pm 30 min), 1300 (\pm 30 min), and 1700 (\pm 30 min); each meal is to be consumed within 15 minutes. On Day 35, as part of the MMTT, a standardised liquid meal is to be given to subjects in the morning at 0800 (\pm 15 min). Following the MMTT, subjects will be given standardised solid meals for lunch (1400 \pm 5 min) and evening meal (1800 \pm 5 min). Note that the time of standardised meals may be adjusted \pm 1 hr provided all other related procedures are performed at the same time intervals. On Day 35 after the evening meal at 1800 (\pm 5 min), subjects should remain fasted overnight for 14 hours until after the T=24h MRS scan and predose laboratory assessments are performed on Day 36. Subjects are permitted to drink normal water during this period. On Day 36, after the final MRS at 0800 (\pm 15 min), the subject may resume their normal diet.

^j Deuterated water should be administered on Day 34 at 1800 and 2200 (\pm 15 min). The subject should then avoid drinking any additional water until 0800 the next morning. Subjects are permitted to drink small quantities of deuterated water during the fast if thirsty. Note that the start time of the deuterated water administration may be adjusted to 1 hr before or 1 hr after provided all other related procedures are performed at the same time intervals.

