^k Following a minimum 14-hour fast, a MMTT will be performed at 0800 (\pm 15 min) on Day 35. Baseline samples will be collected at T = 0 (alongside samples for other blood tests and 2H labelled glucose); a standardised liquid meal will be given to subjects and should be consumed in entirety within 5 min. Further blood samples will be collected at T = 15, 30, 45, 60, 120, 180 and 220 min (\pm 5 min) for 2H labelled glucose levels. Note that the start time of the MMTT may be adjusted \pm 1 hr after provided all other related procedures are performed at the same time intervals.

^l MRS scans will be performed on Day 35 at 0700, 1300 and 2200 (\pm 15 min) and on Day 36 at 0800 (\pm 15 min). Note that times may be adjusted to \pm 1 hr provided all other related procedures are performed at the same time intervals. The MRS scan that will be used to evaluate liver fat content should be performed whilst the subject is fasted and may occur on Day 35 or Day 36.

^m Investigational product administration should occur at home by the subject on Day 9 through 32 and in the clinic at 0800 (\pm 60 min) on Day 33, Day 34, and Day 35. Note that times may be adjusted to \pm 1 hr on Day 35 provided all other related procedures are performed at the same time intervals. Investigational product should be administered on Day 35 just after blood samples have been collected for PK, ADA, 2H labelled glucose, gluconeogenic substrates, and non-genetic research.

ⁿ Investigational product will be dispensed on Day 33

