3.2 Analysis Populations

The analysis populations are defined in [Table 3.2-1](#).

Table 3.2-1 Analysis Populations

Population	Description
Intent-to-treat (ITT) population	Subjects who receive any study investigational product will be included in the ITT population and subjects will be analyzed according to their randomized treatment group.
As-treated population	Subjects who receive any study investigational product will be included in the as-treated population and subjects will be analyzed according to the treatment they actually received.
Pharmacokinetic population	The PK population includes all subjects who received at least one dose of investigational product and had at least one PK blood sample taken that is above the lower limit of quantitation.

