3.4.1.2 Handling of Dropouts and Missing Data

Since there is only one post-baseline measurement MRS, subjects who do not have a valid baseline evaluation or a valid Day 28 (Part A) and Day 35 (Part B) MRS evaluation at 4 hours (Part A) and 24 hours (Part B) post standardized morning meal will not contribute to the analysis.

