3.4.1.3 Primary Efficacy Analysis

The primary efficacy analysis will be performed using the ITT population.

The primary endpoint, change in hepatic glycogen concentration (measured by MRS, adjusted for liver volume) at T = 4 hours post standardized morning meal from baseline (Day -1) to the end of 28 days of treatment will be analyzed using an analysis of covariance (ANCOVA) model with baseline covariate and treatment group. Pairwise comparisons between MEDI0382 and placebo will be performed within this analysis (Part A only).

The primary endpoint, percentage change in fasting hepatic glycogen concentration (adjusted for liver volume) as measured by MRS at T=24 hours post standardized morning meal from baseline (Day 1) to the end of 35 days of treatment (Day 36), will be compared between the MEDI0382 and placebo groups using an analysis of covariance (ANCOVA) model adjusting for baseline value and treatment group (Part B only).

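### Does the undefined word valid in SAP 3.4.1.2 leave the Part B primary analysis set open?

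*SAP*

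**What the plan says.** SAP 3.4.1.2 removes from the primary analysis "subjects who do not have a valid baseline evaluation or a valid Day 28 (Part A) and Day 35 (Part B) MRS evaluation". The scan meant is the one taken 4 hours (Part A) or 24 hours (Part B) after the morning meal. The SAP uses the word *valid* again for baseline in 3.1 and defines it in neither place. Protocol 4.3.1.2 sends scan procedure to a study manual that is not among the documents.

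The surrounding rules are these:

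- **Population.** SAP 3.2: "Subjects who receive any study investigational product will be included in the ITT population", analysed by randomised group. SAP 3.4.1.3 runs the primary analysis on that population.
- **Missing data.** SAP 3.1 has all available data analysed, with no imputation outside the AUC calculations.
- **Stopping treatment.** Protocol 4.1.6: "Subjects who are permanently discontinued from receiving investigational product will be followed for protocol-specified assessments", with listed exceptions such as withdrawn consent.
- **Endpoint.** SAP 3.4.1.3: the percentage change "from baseline (Day 1) to the end of 35 days of treatment (Day 36), will be compared between the MEDI0382 and placebo groups".
- **Fast.** The protocol synopsis, for the Day 1 scan: "following an overnight fast of at least 14 hours, subjects will have a final MRS scan performed". Protocol Table 10, for the end of treatment: "Fasting overnight for a minimum of 14 hours required". Table 10 footnote i adds that "subjects should remain fasted overnight for 14 hours until after the T=24h MRS scan and predose laboratory assessments are performed on Day 36".
- **Deviations.** SAP 3.9 summarises and lists important deviations and does not tie them to exclusion.

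**The concern.** The sentence in SAP 3.4.1.2 decides who enters the primary ANCOVA, and two kinds of Part B scan seem to be left open.

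The first is the off-treatment scan. A subject who stops investigational product may still be scanned on Day 36. The ITT definition would keep that scan. The endpoint wording refers to 35 days of treatment, which this subject did not have, so an analyst might call the scan not valid. The situation is plausible. Dose reduction is not permitted (Protocol 3.1.3), vomiting occurred in 8 subjects (32%) in an earlier 41-day cohort (Protocol 1.4), and Part B was altered after Part A for tolerability (Protocol 9.2). With a half-life of 8 to 13 hours (Protocol 3.2.1), a week off drug is 168/13 = 13 to 168/8 = 21 half-lives.

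The second is the short fast. The protocol's meal and scan windows allow slightly less than the 14 hours it asks for.

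If either question were settled after the data had been seen, the primary analysis set would not be prespecified, and in arms of about 10 a few subjects can move a p-value across the threshold.

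**Working it through.** **Inputs.** Protocol synopsis, sample size: Part B difference 24.2, SD 17.0, 10 completers per arm, two-sided alpha 0.05. SAP 3.1 default alpha: 0.1. Protocol Tables 9 and 10: evening meal 1800 ± 5 min, scan 0800 ± 15 min. Protocol 3.1.1: a scan lasts about 40 minutes. Assumed, because the documents give no figure: the number k of off-treatment MEDI0382 scans, and the share of effect they retain (0% or 50%). No baseline covariate is used, because no baseline correlation is given.

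**Step 1: the plan's own figure.** Noncentrality = 24.2 / (17.0 × √(2/10)) = 24.2 / 7.60 = 3.18 on 18 df. Power = 0.853 (0.889 by normal approximation). The stated figure of more than 80% is reproduced. The smallest significant difference is 2.101 × 7.60 = 16.0 points at alpha 0.05, and 13.2 at alpha 0.1.

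**Step 2: which reading the text supports.** SAP 3.1 keeps available data, SAP 3.2 keeps every dosed subject as randomised, SAP 3.4.1.3 applies that population, and no other efficacy set is defined. No passage links validity to dosing status. SAP 3.4.1.2 is the rule on dropouts and missing data, so there *valid* reads most naturally as a measurement that exists and can be used.

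**Step 3: size if an analyst excluded off-treatment scans instead.** Protocol 3.1.2 recruits so that about 10 subjects per arm complete dosing, with at most 35 randomised. The frame closest to the plan therefore adds k off-treatment subjects to 10 completers. Expected difference with them included, no effect retained: 24.2 × 10/(10 + k). Simulated t-tests at alpha 0.05:

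| k | Difference, included | Power, included | Power, excluded | Verdicts differ | Differ, half effect kept |
|---|---|---|---|---|---|
| 1 | 22.0 | 77% | 85% | 9% | 5% |
| 2 | 20.2 | 70% | 85% | 17% | 8% |
| 3 | 18.6 | 62% | 85% | 24% | 9.5% |

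A harsher frame places the k subjects inside the 10. The expected difference is then 24.2 × (10 − k)/10:

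| k | Difference, included | Power, included | Power, excluded | Verdicts differ | Differ, half effect kept |
|---|---|---|---|---|---|
| 1 | 21.8 | 74% | 83% | 10% | 6% |
| 2 | 19.4 | 61% | 80% | 21% | 10% |
| 3 | 16.9 | 47% | 77% | 31% | 14% |

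At alpha 0.1 with no effect retained, verdicts in the harsher frame differ in about 7%, 15% and 25% of trials.

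**Step 4: data exactly as planned, no effect retained.** In the harsher frame the pooled variance with the scans included is [9 × 17² + 24.2² × k(10 − k)/10 + 9 × 17²] / 18. For k = 3 this is (2601 + 1229.8 + 2601)/18 = 357.3, SD 18.9, t = 16.94 / (18.9 × √0.2) = 2.00, p = 0.060. For k = 1 and 2, p = 0.014 and 0.031. With the scans excluded, p = 0.007, 0.009 and 0.011. In the added frame the same calculation, with 10 + k MEDI0382 subjects, gives p = 0.011, 0.019 and 0.028 with the scans included, all below 0.05.

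**Step 5: the fast.** Shortest in-window fast, meal to start of scan: 0745 − 1805 = 13 h 40 min. Longest: 0815 − 1755 = 14 h 20 min. The largest shortfall is 20 minutes in 840, or 2.4%. Footnote i runs the fast until after the scan. Timed to the end of a 40-minute scan, the shortest fast is 13 h 40 min + 40 min = 14 h 20 min, so every in-window scan meets 14 hours. The documents give no glycogen change per hour of fasting, so no effect on the estimate can be derived. The windows are the same for both arms.

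**Step 6: the labels.** Table 10 footnote l: "MRS scans will be performed on Day 35 at 0700, 1300 and 2200", with the remaining scan at 0800 on Day 36. No Day 35 scan falls 24 hours after the Day 35 meal, so the 24-hour value named in SAP 3.4.1.2 can only be the Day 36 scan, as SAP 3.4.1.3 says. The SAP's remark that there is a single post-baseline measurement is true of each primary endpoint, though not of scans in general.

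**The case for a change.** The strongest case for a change is that two careful analysts could still differ. One would follow the ITT definition and keep an off-treatment scan. The other would point to the endpoint's 35 days of treatment and drop it. Nothing in the SAP says outright that the first is right, and no sensitivity analysis shows the other result. If the effect in treated subjects were nearer 18 points than 24.2, one off-treatment scan among the 10 would be enough to matter (p = 0.053 included, 0.034 excluded). A definition would cost a few sentences.

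Part of this stands. The word is undefined, the arithmetic is correct, and the endpoint wording pulls slightly against the population rule. Three things limit it:

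- The endpoint wording names the time of measurement. It is not an exclusion rule, whereas SAP 3.1 and 3.2 are explicit rules on data and population, and both point to inclusion.
- The up to 5 replacements in Part B (Protocol 4.1.7) are for subjects who leave the study. After withdrawal of consent no further data are collected (Protocol 4.1.5), so such subjects have no later scan. The replacement allowance therefore gives no count of off-treatment scans.
- Technical quality rules may sit in the study manual or the programming plan, and the text of Protocol 4.2.3.1 on early discontinuation visits is not available in the copy reviewed.

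The sensitivity to k shows that inclusion and exclusion answer different questions. It does not show that the reading the SAP supports is wrong.

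**Conclusion.** No change follows. The missing definition is a gap that analysts can fill from the SAP's own rules: analyse every usable scan from dosed subjects in the group to which they were randomised, including those who stopped treatment. Followed that way, the planned ANCOVA gives a sound answer for the ITT population, and writing out a definition would record that reading without correcting the method.

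The cost of a different reading is moderate and conditional. With 1 to 3 off-treatment MEDI0382 scans added to 10 completers per arm, verdicts at alpha 0.05 differ in about 9% to 24% of trials if no effect remains, and about 5% to 9.5% if half remains. If the scans fall within the 10, the ranges are about 10% to 31% and 6% to 14%. The number of scans and the retained effect are assumed throughout, and the baseline covariate is left out.

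The short-fast part has no demonstrated effect: the shortfall is at most 20 minutes, and no passage makes the fast a test of validity. The Day 35 label and the remark about a single measurement are clerical and leave no doubt about which scan is analysed.

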3.4.1.3 Primary Efficacy Analysis

The primary efficacy analysis will be performed using the ITT population.

The primary endpoint, change in hepatic glycogen concentration (measured by MRS, adjusted for liver volume) at T = 4 hours post standardized morning meal from baseline (Day -1) to the end of 28 days of treatment will be analyzed using an analysis of covariance (ANCOVA) model with baseline covariate and treatment group. Pairwise comparisons between MEDI0382 and placebo will be performed within this analysis (Part A only).

The primary endpoint, percentage change in fasting hepatic glycogen concentration (adjusted for liver volume) as measured by MRS at T=24 hours post standardized morning meal from baseline (Day 1) to the end of 35 days of treatment (Day 36), will be compared between the MEDI0382 and placebo groups using an analysis of covariance (ANCOVA) model adjusting for baseline value and treatment group (Part B only).

3.4.2 Secondary Efficacy Endpoint(s) and Analyses

3.4.2.1 Secondary Efficacy Endpoint(s)

- Percentage change in fasting hepatic glycogen concentration adjusted for liver volume as measured by MRS at T = 24 hours post standardized morning meal from baseline (Day -1) to the end of 28 days of treatment (versus placebo, Part A only)
- Percentage change in fasting hepatic glycogen concentration adjusted for liver volume as measured by MRS at T = 24 hours post standardized morning meal from baseline (Day 1) to the end of 35 days of treatment (versus liraglutide, Part B only)
- Change in hepatic fat fraction from baseline as measured by magnetic resonance imaging (Day -1) to the end of 28 days of treatment (Part A only)
- Change in hepatic fat fraction from baseline as measured by magnetic resonance imaging (Day 1) to the end of 35 days of treatment (Part B only)
- Measures of safety and tolerability (vital signs, ECGs, laboratory test results, AEs)
- Development of ADA and titre (if confirmed positive)

3.4.2.2 Secondary Efficacy Analyses

The secondary efficacy analyses will be performed using the ITT population.

The percentage change in fasting hepatic glycogen concentration (measured by MRS, adjusted for liver volume) at T = 24 hours post standardized morning meal from baseline (Day 1) to the end of 35 days of treatment, will be compared between MEDI0382 and liraglutide groups only in Part B of the study. This will be done using the ANCOVA model adjusting for baseline value and treatment group. A similar analysis will be applied to measure change in hepatic fat fraction from baseline (Day -1 or Day 1) to the end of 35 days of treatment (Day 35 or 36) versus placebo (Part B only).

The percentage change in fasting glycogen concentration (measured by MRS, adjusted for liver volume) at T = 24 hours post standardized morning meal from baseline (Day -1) to the end of 28 days of treatment, will be compared between MEDI0382 and placebo groups only in Part A of the study. This will be done using the ANCOVA model adjusting for baseline value and treatment group. A similar analysis will be applied to measure change in hepatic fat fraction from baseline (Day -1) to the end of 28 days of treatment versus placebo (Part A only).

